9.1.2. Initiation visit

All clinical investigation sites will get an on-site initiation visit during which full training on all aspects of the clinical investigation and the investigational device will be provided.

9.1.3. Monitoring visits

The site dedicated monitor is to ensure adherence to the clinical investigation plan, accurate data recording on the eCRFs and to monitor recruitment rates and adherence to follow-up schedules. The principal investigator shall permit and assist the monitor to carry out verification of completed eCRFs against data in the source documents.

The principal investigator can delegate tasks to his/her collaborators, however the roles and responsibilities and time period of involvement for each clinical site personnel must be documented on the delegation log as well as training received before getting involved with the clinical investigation must be documented in the training log.

The monitor shall inform the sponsor about any problems relating to facilities, technical equipment or medical staff at the clinical investigation site. During the clinical investigation, monitors shall check that appropriate written informed consents have been obtained. The monitor shall also be responsible for notifying such deficiencies in writing to the principal investigator and convene with the clinical investigation site personnel appropriate and timely corrective actions.

Written informed consent, in- and exclusion criteria and all AEs occurring in the investigation will be 100% verified for timely completion for all subjects enrolled in the investigation.

Investigation Site File shall be monitored for 100% completion per the Investigation File Requirement Checklist.

The monitor shall make written reports to the sponsor, after each visit and provide written action items if any, to the principal investigator or clinical investigation site personnel.

The first monitoring visit at the site should be conducted as soon as reasonably possible after the first subject(s) has(have) completed the first visit of the investigation. This is to minimise systematic errors done by site and to clarify potential questions before proceeding with enrolment of more subjects.

Additional monitoring will be conducted in accordance with the recruitment rate or if there is a need for more frequent visits upon request from site or Clinical Manager.

The monitor will have close contact to the site in the recruitment period to ensure that any concerns, problems or recruitment challenges are solved with the site in a timely manner.

Close-out visit will be performed when all subject visits have been finalised, queries have been solved and database locked.

10.3. LARS score and Quality of Life questionnaires

LARS score questionnaire

Item values (5 items) will for each subject, be summarised to a LARS score with a LARS interpretation as stated below.

Interpretation:

- 0-20: No LARS
- 21-29: Minor LARS
- 30-42: Major LARS

Symptom-related Quality of Life questionnaire (modified FIQL)

The FIQL scale is thus interpreted for four scales exploring different aspects of the patient's quality-of-life:

- Lifestyle (10 items) 2A, 2B, 2C, 2D, 2E, 2G, 2H, 3B, 3L, 3M
- Coping/behavior (9 items) 2F, 2I, 2J, 2K, 2M, 3C, 3H, 3J, 3N
- Depression/self-perception (7 items) 1, 3D, 3F, 3G, 3I, 3K, 4
- Embarrassment (3 items) 2L, 3A, 3E

The quality-of-life score is analysed for each scale. There is not a global score.

Items are scored 1 (least satisfactory quality-of-life) to 4 (most satisfactory quality-of-life). Specifically, prior to estimating the Depression/self-perception scale, in question no. 1, "Excellent"/"Excellent" must be scored 5 and "Poor"/"Mauvaise" must be scored 1 (11).

The score for each scale is calculated by dividing the sum of the item scores by the number of items.

If data is missing for a given item, it is assigned a value equal to the average of the other items in the scale. If data are missing for half or more than half of the items, the scale cannot be interpreted.

EQ-5D-5L questionnaire

[figure not shown]
There should be only ONE response for each dimension. Missing values are preferably coded as '9'. Ambiguous values (e.g. two boxes are ticked for a single dimension) should be treated as missing values.

Each of the five dimensions comprising the EQ-5D descriptive system (mobility, self-care, usual activates, pain/discomfort, anxiety/depression) is divided into five levels:

- LEVEL 1: indicating no problem
- LEVEL 2: indicating slight problems
- LEVEL 3: indicating moderate problems
- LEVEL 4: indicating severe problems
- LEVEL 5: indicating unable to/extreme problems

A unique health state is defined by combining one level from each of the five dimensions. i.e. state 12345 indicates no problems with mobility, slight problems with washing or dressing, moderate problems with doing usual activities, severe pain or discomfort and extreme anxiety or depression, while state 11111 indicates no problems on any of the five dimensions.

Following endpoints ():

Following endpoints (proportions):

- Number of subjects with Major LARS (≥ 30)

Will be analyzed, by a non-parametric chi-square test using proc FREQ in SAS. A test of H0 (no association) will be performed.

Following endpoints

Following endpoints:

- The number of adverse events
-
-

Will be reported by descriptive statistics

Data obtained from the diary includes a run-in period of 14 day starting from visit 1. Analysis and descriptive statistics pertaining to diary data will not include the run-in period.

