5.1. General

This investigation is a randomised, open-label, comparative, parallel, post market study. In total, 34 rectal resection subjects with major LARS will be included and randomised, and each subject will have an inclusion visit and two test visits and follow-up phone calls in between. Each subject will be enrolled for a study duration of 12 weeks. Subjects will be randomized to the treatments stratified by neo-adjuvant radiotherapy. Training will be performed at the randomisation visit V1. If needed, patients may have additional training sessions before being able to perform the irrigation on their own. After the training sessions the study duration is 12 weeks.

[figure not shown]

Figure 1 Design of the randomised clinical study

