5.7. Randomisation Procedure

As this is a parallel investigation, subjects are assigned to one treatment in a 1:1 allocation ratio, where each subject will be randomized into one of two treatment arms i.e. investigational device and comparator.

At visit 1 investigator or his representative, as per the randomisation list, allocates a randomisation treatment code to each patient. The randomisation code is recorded in the electronic Case Report Form (eCRF) by investigator or his representative.

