First visit Information visit	If an eligible subject is interested in participating, baseline visit (V0) will be arranged. When arranging the visit, it will be ensured, that the subject has received the Subject Information prior to the visit. The subjects will receive both written and verbal information about the possibility of bringing a companion to the informational visit and to any possible subsequent visits. See section 16. for information to be given to the subjects, as well as the informed consent process.
Enrolment and Baseline visit (V0)	The subjects will be offered at least 24 hours to think about if they will participate, or if they wish to give consent right away. If/when the subject decides to participate, he/she will be asked to sign the relevant forms (see section 16). If a subject so desires, and it is certain that it is understood what the investigation entails, and the relevant forms have been signed the subjects are considered enrolled in the investigation.

- Instruct subject in completing subject diaries
- Instruct subject in use of the investigational devices/standard of care
- Instruct and remind the subject to follow the study specific procedures between visits
- Schedule next visit in 12 weeks

Phone call (twice a week for the first 3 weeks; 6 phone calls, 30 mins):

- Give support in the use of the investigational device/standard of care
- Remind the subject to complete diaries
- Complete eCRF
- Registration of AEs/ADEs/SAEs/SADEs
- Remind the subject to follow the study specific procedures between visits

Termination visit (V2) after 12 weeks (\pm 4 days):

- Complete eCRF
- Complete QoL questionnaires
- Registration of AEs/ADEs/SAEs/SADEs
- Review AEs/ADEs/SAEs/SADEs
- Collect subject diaries
- Collect investigational device
- Fill in termination form

Assessment(s)						
On-site visit • LARS score Questionnaire • FIQL score Questionnaire • EQ – 5D – 5L • Satisfaction with treatment • [REDACTED]	Subject/Investigator (All)		X			X
On-site visit • [REDACTED] • [REDACTED]	Subject/Investigator (Peristeen Cone only)					X
Subject diary: • [REDACTED] • [REDACTED] • [REDACTED]	Subject (All) Run-in period (14 days from Visit 1)		X	X		
Subject diary: • [REDACTED]	Subject (Peristeen Cone only)			X		
Device training	Investigator		X			
AE/SAE reporting			X		X	X
Registration of termination						
Termination form	Investigator					X

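### Does leaving the first 14 days after randomisation out of the diary summaries distort the trial's results?

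*Combined protocol and SAP*

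**What the plan says.** The statistical text after section 10.3 defines the window and then sets it aside: "Data obtained from the diary includes a run-in period of 14 day starting from visit 1", followed by "Analysis and descriptive statistics pertaining to diary data will not include the run-in period". The exclusion therefore covers descriptive tables as well as tests.

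Two other places fix what visit 1 is. Section 5.1 states: "Training will be performed at the randomisation visit V1". Section 5.7 states: "At visit 1 investigator or his representative, as per the randomisation list, allocates a randomisation treatment code to each patient".

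The assessment schedule (printed after section 6.2) assigns the run-in diary to both arms: "Subject (All) Run-in period (14 days from Visit 1". A separate diary row applies to the device arm only. Support calls are made "twice a week for the first 3 weeks; 6 phone calls, 30 mins", and one task at each call is "Remind the subject to complete diaries". Subjects are thus asked to keep the diary during the window that is later left out.

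**The concern.** A run-in normally precedes randomisation, and dropping it costs nothing. Here the label is attached to the first two weeks of randomised, open-label treatment. Two things could follow.

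- **Selection.** Diary results from day 15 come only from subjects still keeping a diary after a fortnight of their allocated treatment. If early stopping differed between arms and was related to how treatment was going, a between-arm diary comparison would no longer be protected by randomisation.
- **Reporting.** A subject whose diary ends by day 14 would appear in no diary table, and early experience with the device would not be described. With 17 subjects per arm, one or two such subjects could be noticeable.

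The available text gives no reason for the exclusion and no companion summary over the full period.

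**Working it through.** **Inputs.** Run-in of 14 days from visit 1 (text after section 10.3). Termination visit at 12 weeks ± 4 days, that is 84 days, range 80 to 88 (visit description after section 6.2). Mean difference 7, SD 6, 13 completers and 17 randomised per arm, about 20% drop-out (section 10.6).

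**The plan's own figure.** Taking two-sided 5% (an assumption, as the available text does not state alpha), two-sample t-test power is 78.0% with 12 per group and 81.4% with 13. So 13 is the smallest number reaching 80%. Then 13 / 0.8 = 16.25, rounded up to 17 per arm and 34 in total. The sample size reproduces, and the diary rule does not enter it.

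**Share of follow-up left out**, if the diary is kept daily to the end (the available text gives no frequency or end date):

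- Nominal: 14 / 84 = 16.7%, leaving 70 days.
- Over the visit window: 14 / 88 = 15.9% to 14 / 80 = 17.5%.
- In diary-days for 34 subjects: 34 × 14 = 476 of 34 × 84 = 2,856.

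**Subjects who might have no diary data after day 14.** The documents do not say. If only the planned drop-outs stopped, the ceiling is 17 − 13 = 4 per arm, so 0 to 4 of 17 (0% to 23.5%). Spreading those four evenly over 84 days gives 4 × 14 / 84 = 0.67 per arm by day 14. That evenness is assumed, because no drop-out timing is given. A subject can also stop the diary and stay in the trial, so even the ceiling is not firm. None of these figures measures bias.

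**What depends on the diary.**

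| Item | Source | Affected by the exclusion? |
|---|---|---|
| LARS score (primary) | Questionnaire at termination | No |
| Major LARS, FIQL, EQ-5D-5L, satisfaction | On-site visit assessments at termination | No |
| Adverse events | Recorded at visits and at the early calls | No |
| Success criterion (section 10.8) | Primary endpoint | No |
| Diary items | Diary; names blacked out | Yes |

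A biased comparison needs three conditions together: a diary item compared between arms, some subjects without diary data after day 14, and a difference between arms in who they are. The documents establish none of the three.

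**Would including days 1 to 14 repair the selection?** Not really. A subject who stops by day 14 has no later diary under either rule, so the gap comes from stopping and not from the exclusion. A full-period average would represent that subject by adaptation days alone and others mostly by later days, which is a different quantity and no cleaner a comparison.

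**The case for a change.** The strongest opposing case is that a wish to study established use may justify an analysis from day 15, but does not explain removing the first fortnight from the descriptive tables too. The window also fits a learning period imperfectly. It is fixed from visit 1, while section 5.1 allows further training sessions afterwards, and it removes control-arm days although formal device training belongs to the other arm. Tables for days 1 to 14 would be cheap, since the data are collected anyway.

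Much of this stands as fact: the label is a misnomer, the window is not tailored to the individual, and the available text offers no reason. It does not amount to a defect, for four reasons.

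- A common fixed window is simple and cannot be adjusted after seeing results. Tailoring it to each subject's training would make the analysis period depend on allocation.
- Both arms receive instruction at visit 1 and telephone support in the first three weeks, so a settling-in period for both is plausible. For the same reason the idea that the rule favours the device is unsupported.
- Section 20 commits the clinical investigation report to evaluating all the data collected. It promises no specific table, but it argues against reading the rule as withholding data.
- The contents list sections 5.4 and 5.5 on exploratory endpoints and the rationale for endpoints, and neither is in the available text. The absence of a stated reason cannot be held against the plan.

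**Conclusion.** The factual reading is right: the 14 days are post-randomisation, apply to both arms, and are not planned for diary analysis or description in the available text. No change is called for. The exclusion is prespecified, symmetric and a fair trade-off for describing settled use. It affects only blacked-out, apparently exploratory diary items, and no visible endpoint, comparison or success criterion rests on them.

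The size is 14 of 84 days (16.7%; 15.9% to 17.5% over the visit window), assuming diaries run to the termination visit. The number of subjects affected is unknown, and no direction of bias can be stated. Calling the window a post-randomisation adaptation period, and adding a by-arm description of days 1 to 14 with a count of subjects lacking later diary data, is an option for the report's authors. The day-15-onward analysis would stay as it is, and no visible conclusion would move. The judgement would need revisiting only if the blacked-out text made a diary item the basis of a between-arm claim.

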10.6. Sample size

The purpose of the study is to demonstrate superiority of the test product in the primary endpoint.

A sample size of 34 subjects (26 completers), assuming a drop-out rate of approximately 20%, gives sufficient power to demonstrate superiority of the test product. See Table 4 and Figure 2 for graphical presentation of the power and sample size, under varying values of mean difference.

Table 4 Power and sample size

minimal mean difference in LARS score of 7 between treatments (Peristeen cone and standard of care) is deemed clinically relevant.

The assumption of SD=6, is based on data provided by Martellucci et al., 2018 (13). Hence, the effective number of subjects needed to obtain approximately 80% power is 13 per group (17 subjects assuming a 20% drop-out rate).

10.8. Pass/fail criteria

The success criterion is to demonstrate superiority of the Peristeen Cone device in the primary endpoint.

10.9. Interim analysis

No interim analysis is planned for this study.

10.9. Statistical reason for termination of investigation

There is no reason to terminate the investigational study based on statistical considerations.

10.10. Deviation(s) from statistical design, method or analytical procedures

Any deviations from the statistical plan will be documented in the clinical Investigation Report.

11. Data management

11.1. Data Collection in the clinical investigation

Data management and the final statistical analyses of all measurements described in this protocol are carried out by the ██████████ Coloplast A/S.

Data will be collected through an electronic data capturing (EDC) system on electronic Case Report Form (eCRF), a secure, internet-based case report form and on paper CRF for QoL questionnaires and subject diaries and entered into the electronic data capturing system. This system will be used to record all subject information collected in the investigation for secure data tracking and centralised data monitoring ("remote monitoring") done by monitors, as defined in the monitoring plan.

The EDC system used is ██████████ delivered by ██████████. The system is designed to be compliant with the FDA requirements of 21 CFR part 11. It is a validated data management system allowing only qualified and trained personnel to enter the system. The system has full audit trail and electronic signature.

The sponsor will be responsible for training the investigator, or delegate, in completion of the eCRF and pCRF.

Principal Investigator, or delegate, at the clinical site will perform primary data collection directly into the eCRF or drawn from source-document (medical records) reviews. The eCRF will be completed on a continuous basis starting from the point of enrolling the subject to final follow up.

The eCRF will be completed by the investigator, or delegate, who have signed the Site Personnel Signature and Delegation List and Clinical Investigation Training Log. It will be the responsibility of the investigator to ensure that all measurements and observations are correctly noted in the eCRF.

All assessments and observations throughout the investigation for each subject must be carefully recorded in an eCRF during the visit or immediately after. The eCRF makes it possible to enter data right away when they

- Monitor data quality through routine review of submitted data in real-time to identify missing data, inconsistent data, data outliers, and potential protocol deviations that may be indicative of systemic and/or significant errors in data collection and reporting at the site
- Verify source data remotely, provided that both source data and CRFs can be accessed remotely
- Conduct aggregate statistical analyses of study data to identify subject data that are outliers relative to others and to evaluate individual subject data for plausibility and completeness
- Conduct analyses of site characteristics, performance metrics (e.g., high screen failure rates, high frequency of eligibility violations, and delays in reporting data), and clinical data to identify early on corrective actions needed for characteristics correlated with poor performance or noncompliance

11.3. Data retention

The Investigator file must be archived for a minimum period of 15 years after the final clinical investigation report has been signed.

All investigation site documents must be archived for a minimum period of 15 years after the final clinical investigation report has been signed. The monitor is responsible for informing the investigator and the CM if this period should be longer for their sites according to local regulation.

12. Amendments to the Clinical Investigation Plan

No changes in the clinical investigation procedures shall be affected without mutual agreement between the principal investigator and the sponsor. The agreement of the changes must be documented by signing the corresponding clinical investigation plan amendments and registered in the Change Log.

All significant changes require notification to the EC and applicable regulatory authority. Substantial changes may require approval from the EC and applicable regulatory authority prior to implementation.

13. Deviations from the Clinical Investigation Plan

Deviations to the Clinical Investigation Plan occurs when the activities during the clinical investigation do not comply with the EC approved investigation plan. A minor deviation is defined as those that don't increase risk or decrease benefit or don't have a significant effect on the subject's rights, safety or welfare; and/or on the integrity of the data.

The investigator is not allowed to deviate from the Clinical Investigation Plan unless, under emergency circumstances or to protect the rights, safety and welfare of the subject(s).

For the purposes of this investigation, any variance from the protocol is considered a deviation and is to be reported.

The site will complete a deviation eCRF for all data-related deviations and all deviations that are not related to the data for example, an untrained nurse performing study procedures are reported in the Deviation Log located in the Investigator File.

If any deviations to the investigation plan are detected during the monitoring visit, the Monitor shall ensure the site reports all deviations in the eCRF or on the Deviation log in the Investigator File. Additionally, the monitor must report any deviation noted during the visit in the Periodic Monitoring Report.

Monitor will align with data management in each investigation, how data management will be informed about all deviations.

The following information about the deviation will be collected:

- Site (site ID), Subject (subject ID)

15.2. Data protection

As part of the investigation Coloplast A/S, [name] ("Coloplast") will collect and process the personal information the subject provides for the investigation ("subject personal data"). This includes identification and contact information (which may be pseudonymised) as well as information about product usage experience and your health. Coloplast will only process the subject's personal data:

1. To conduct the investigation and carry out related research based on subject consent (primary use), cf. article 9(2)(a) of the EU General Data Protection Regulation (GDPR),
2. To comply with applicable legal obligations to e.g. ensure reliability and safety, cf. article 6(1)(c) in conjunction with article 9(1)(i) of GDPR, and
3. If separate consent is given for secondary use of subject personal data, cf. article 9(2)(a) of GDPR –carry out research outside the clinical protocol to improve Coloplast's products and services, and for use in education.

Part of Coloplast's processing is carried out on third-party platforms (clinical trial databases) and certain third parties are assisting Coloplast in the processing (e.g. the investigator). Such cases will imply a transfer of your personal data to the third parties, but solely for the specified purposes and with the third parties acting on instruction from Coloplast. Data may be collected and processed across the Coloplast network, which may entail processing of personal data outside the European Economic Area. In such cases, an adequate level of protection will be ensured by the third parties being subject to the standard contractual clauses on data protection adopted by the EU or to an EU-approved certification mechanism on data protection. For further information about this please the subject can always consult Coloplast's data protection officer (details below).

Subject personal data will be kept as long as required under applicable laws and regulations. The EU Medical Device Regulation obligates Coloplast to keep the data for a period of at least 15 years after the investigation is completed, or, in the event that the device is subsequently placed on the market, at least ten years after the last device has been placed on the market. Subject personal data will be deleted at the end of the mandatory retention period.

If the subject has questions or queries regarding Coloplast's handling of personal information, the subject can always contact Coloplast's Data Protection Officer at [REDACTED]. Complaints related to Coloplast's handling of subject personal information may similarly be sent to the Data Protection Officer, and the subject are also entitled to file a complaint with the relevant supervisory authority, which in the case of France is the French Data Protection Agency: CNIL (<https://www.cnil.fr/fr/plaintes>).

The subject can write to [REDACTED] any time to request:

- Access to personal data
- Correction of errors in personal data or to erase personal data
- Limit what can be done with personal data
- To receive personal data in machine-readable format (data portability).
- Withdrawal of consents the subject has given Coloplast to process personal data

